CD4 Lymphocyte count at baseline	The patient has CD4 Lymphocyte count results at baseline (+ or - 4 weeks) of TAF/FTC/BIC therapy.	Qualitative	0: No 1: Yes	
CD4 Lymphocyte count at baseline value	CD4 Lymphocyte count value at baseline (+ or - 4 weeks) of therapy with TAF/FTC/BIC	Cuantitativa, continua	1, 1.5, 1.8, 2, n	

CD4 Lymphocyte count at week 24	The patient has CD4 Lymphocyte count results at week 24 (+ or - 2 weeks) of TAF/FTC/BIC therapy.	Qualitative	0: No 1: Yes	
CD4 Lymphocyte count value at week 24	CD4 Lymphocyte count value at week 24 (+ or - 2 weeks) of therapy with TAF/FTC/BIC	value at week 24 (+ Quantitative, with TAF/FTC/BIC continuous		
CD4 Lymphocyte count at week 48	The patient has CD4 Lymphocyte count results at week 48 (+ or - 2 weeks) of TAF/FTC/BIC therapy.	0: No 1: Yes		
CD4 Lymphocyte count value at week 48	CD4 Lymphocyte count value at week 48 (+ or - 2 weeks) of therapy with TAF/FTC/BIC	Quantitative, continuous	1, 1.5, 1.8, 2, n	
HDL at baseline	The patient has high-density lipoprotein results at baseline (+ or - 4 weeks) of TAF/FTC/BIC therapy	Qualitative	0: No 1: Yes	
HDL value at baseline	High-density lipoprotein value at baseline (+ or - 4 weeks) of TAF/FTC/BIC therapy	Quantitative, continuous	1, 1.5, 1.8, 2, n	
HDL at week 24	The patient has high-density lipoprotein		0: No 1: Yes	
HDL value at week 24	High-density lipoprotein value at week 24 (+ or - 2 weeks) of TAF/FTC/BIC therapy	Quantitative, continuous	1, 1.5, 1.8, 2, n	
HDL at week 48	The patient has high-density lipoprotein results at week 48 (+ or - 2 weeks) of TAF/FTC/BIC therapy.	0: No 1: Yes		
HDL value at week 48	High-density lipoprotein value at week 48 (+ or - 2 weeks) of TAF/FTC/BIC therapy	Quantitative, continuous	1, 1.5, 1.8, 2, n	
LDL at baseline	The patient has low-density lipoprotein results at baseline (+ or - 4 weeks) of TAF/FTC/BIC therapy.		0: No 1: Yes	
LDL value at baseline	Low-density lipoprotein value at baseline (+ or - 4 weeks) of TAF/FTC/BIC therapy	Quantitative, continuous	1, 1.5, 1.8, 2, n	
LDL at week 24	The patient has low-density lipoprotein HDL results at week 24 (+ or - 2 weeks) of TAF/FTC/BIC therapy.	Qualitative	0: No 1: Yes	
LDL value at week 24	Low-density lipoprotein HDL value at week 24 (+ or - 2 weeks) of TAF/FTC/BIC therapy	Quantitative, continuous	1, 1.5, 1.8, 2, n	
LDL at week 48	at week 48 The patient has low-density lipoprotein results at week 48 (+ or - 2 weeks) of TAF/FTC/BIC therapy.		0: No 1: Yes	

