Number of medication claims	Number of TAF/FTC/BIC medication claims during the 48-week follow-up	Quantitative, discrete	1, 2, 3, n
Headache emergency	nergency The patient visited the emergency department during the period of TAF/FTC/BIC use for ICD-10 codes G444 and/or G448		0: No 1: Yes
Diarrhea emergency	The patient visited the emergency department during the period of TAF/FTC/BIC use for ICD-10 code A09X: Diarrhea and gastroenteritis of presumed infectious origin	ing the period of or ICD-10 code A09X: Qualitative enteritis of presumed	
Nausea and vomiting emergency	The patient visited the emergency department during the period of TAF/FTC/BIC use for ICD-10 code R11X: Nausea and vomiting	Qualitative	0: No 1: Yes
Termination of health insurance coverage	The patient terminated their health insurance with EPS SURA.	Qualitative	0: No 1: Yes
Date of termination of insurance coverage	Date of termination of health insurance with EPS SURA	Quantitative, continuous	dd/mm/yyyy
Death	The patient passed away after the index date	Qualitative	0: No 1: Yes
Date of death	Date of death Date of patient's death		dd/mm/yyyy

Sample Size

No sampling will be conducted, as data from the entire population (census) that meets the eligibility criteria for this study will be used.

Statistical Analysis

The database created in Access will be transferred to RStudio and Jamovi for the corresponding descriptive analysis.

Characterization of the Sociodemographic and Clinical Profile

Absolute and relative frequencies will be calculated for categorical variables. For numerical variables, normality will be assessed using the Shapiro-Wilk test. Variables with a p-value greater than 0.05 will be considered to follow a normal distribution and will be represented by means and standard deviations. For variables that do not follow a normal distribution, medians and interquartile ranges will be used.

Proportion of Pretreatment Regimens

The proportion of patients who have received different combinations of ART prior to starting TAF/FTC/BIC will be calculated. Frequency tables will be used to display the proportion of each pretreatment regimen, supplemented by bar charts reflecting the frequencies of the most common treatments.

Virologic Suppression at 24 and 48 Weeks

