Virologic suppression is defined as a viral load of <50 copies/mL at weeks 24 and 48 of treatment. The proportion of patients achieving this threshold will be calculated at both time points, and the results will be compared between weeks 24 and 48 using McNemar's test for related samples.

Effective Access to Treatment

Effective treatment is defined as the initiation of therapy within a reasonable time after prescription. The time between prescription and the initiation of treatment will be calculated (mean or median, depending on the normality test), and patients will be classified into two categories: those who initiate treatment effectively (within a short period, generally defined as initiation within 7-14 days of HIV diagnosis) and

those who experience delays.

Paraclinical Results: CD4 T-Lymphocytes, Renal Function, and Lipid Profile

To describe changes in clinical markers at weeks 24 and 48, the summary measure (mean or median, depending on the normality test) of baseline values will be compared with the values of these biomarkers at the two time points. Paired-samples t-tests or Wilcoxon tests will be used if the data distribution is non-normal.

Rapid Onset of Therapy

The frequency of patients meeting this criterion will be calculated, and the characteristics of those with rapid onset versus those without will be compared using the chi-square test.

Treatment-Related Adverse Events

Treatment-related adverse events at weeks 24 and 48 will be characterized and classified according to type and severity. The proportion of patients experiencing these events will be calculated and compared between the two time points. Contingency tables and chi-square tests will be used to analyze the relationship between adverse events and other clinical and sociodemographic variables.

Adherence to Treatment

Adherence will be measured using pharmacy claims information with the Proportion of Days Covered (PDC). PDC calculates the proportion of days the patient has access to the medication over a specified period (64,65). In this study, patients with a PDC of 80% or higher will be considered to have adequate adherence. However, studies have shown that even lower adherence levels can still result in a high rate of viral suppression.

Biases

The following biases are considered potential risks in this study:

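### A normality test on each visit's values steers the summary and the paired test for CD4, renal and lipid markers, and no within-patient change with a confidence interval is planned

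*Combined protocol and SAP*

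**What the plan says.** Under Statistical Analysis, Characterization of the Sociodemographic and Clinical Profile: "For numerical variables, normality will be assessed using the Shapiro-Wilk test". The cut-off follows: "Variables with a p-value greater than 0.05 will be considered to follow a normal distribution", with mean and SD as the summary. Otherwise: "For variables that do not follow a normal distribution, medians and interquartile ranges will be used".

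The Variables table lists baseline, week 24 and week 48 values of each marker as separate entries, for example "CD4 Lymphocyte count value at baseline (+ or - 4 weeks) of therapy with TAF/FTC/BIC". It contains no change-from-baseline variable.

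Paraclinical Results says: "the summary measure (mean or median, depending on the normality test) of baseline values will be compared with the values of these biomarkers". This applies to both follow-up visits. The section then adds: "Paired-samples t-tests or Wilcoxon tests will be used if the data distribution is non-normal". It does not say which distribution is meant, and it mentions no estimate of change and no confidence interval.

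Rapid Onset of Therapy says that "the characteristics of those with rapid onset versus those without will be compared using the chi-square test". No between-group test for continuous data is named anywhere in the plan.

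**The concern.** The validity of a paired t-test rests on the within-patient differences. Visit values can be skewed while their differences are close to normal, and the reverse can also happen. A rule defined on visit values therefore looks at a distribution that does not bear on the choice.

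The same rule can also pass a marker at one visit and fail it at another. The reader would then see a mean beside a median, and the gap between them would mix true change with skewness.

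The Specific Objectives ask for the impact of treatment on CD4, renal function and lipids at weeks 24 and 48. What answers that is a change with its uncertainty, and the plan provides for neither. In a study without a comparator, this display is the main evidence a reader will have on these markers.

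**Working it through.** There is no planned sample size, power or effect figure to reproduce, since the Sample Size section describes a census. The documents supply these inputs: the Shapiro-Wilk cut-off of 0.05; three visits per marker; five markers matching the objective (CD4, creatinine, eGFR, HDL, LDL); and at most 169 patients before exclusions and missed laboratory windows (Problem Statement and Relevance). They give no SDs or marker distributions, so every marker shape below is an assumption.

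**1. Exactly normal data, independent tests at 0.05.**
- Two visits classified differently: 2 × 0.05 × 0.95 = 9.5%.
- Three visits not all classified alike: 1 − 0.95³ − 0.05³ = 14.25%.
- At least one of five markers with mixed summaries: 1 − (0.95³ + 0.05³)⁵ = 1 − 0.8575⁵ ≈ 54%. Independence between markers is doubtful, because eGFR is calculated from creatinine, so this is a rough guide.

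**2. Assumed shapes, simulated.** Each cell has 4,000 replicates. The between-visit correlation is 0.7, except in the gamma row, where follow-up is baseline plus normal noise. The per-visit rule is taken to give the t-test only if both visits pass.

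| Assumed shape | Baseline and follow-up classified differently (n = 40 / 80 / 169) | Per-visit rule disagrees with a check on the differences (n = 40 / 80 / 169) |
|---|---|---|
| Normal | 10% / 9% / 9% | 14% / 13% / 13% |
| CD4-like (square root normal) | 46% / 41% / 9% | 62% / 80% / 74% |
| Gamma visits, normal differences | 34% / 34% / 13% | 61% / 87% / 95% |
| Mild lognormal (log SD 0.2) | 32% / 40% / 27% | 41% / 60% / 77% |

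In the three skewed rows the differences passed Shapiro-Wilk in 74-95% of replicates, while both visits passed in only 0-59%. A separate run with milder gamma shapes (20 for LDL, 30 for HDL; n = 60 to 150) gave 24-40% for the first column and 31-65% for the second.

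**3. Size of the display error.** In the CD4-like case, √CD4 has mean 18 and SD 6 at baseline, and mean 22 and SD 5 at follow-up.
- Baseline: mean 18² + 6² = 360, median 18² = 324, gap 36.
- Follow-up: mean 22² + 5² = 509, median 22² = 484, gap 25.
- Consistent displays: means 509 − 360 = 149; medians 484 − 324 = 160.
- Mixed displays: 509 − 324 = 185, or 484 − 360 = 124.

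So the same data can show a rise anywhere from 124 to 185 cells. For the milder shapes the population gap between mean and median is only 1.7% of the mean (0.07 SD) for LDL and 1.1% (0.06 SD) for HDL. With assumed means of 110 and 45, the average distortion when summaries are mixed is about 2-3 units for LDL and 1 for HDL.

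**4. Effect on the test.** The paired t-test and Wilcoxon test disagreed on significance in about 2-3% of LDL- and HDL-like datasets, and in at most 7% across all the settings tried.

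**The case against.** The best defence is that the text is looser than the natural reading. The Shapiro-Wilk rule sits under the heading for the baseline profile, and the phrase about the data distribution does not exclude a check on the differences. The choice of summary is worded in the singular and tied to baseline, so it could mean one choice per marker carried forward. Even if summaries were mixed, the paired test itself would still work on within-patient data. With mildly skewed markers the distortion is modest, and the analysis is described as descriptive.

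Much of this stands. The plan leaves the point open; it does not mandate the wrong check. But the per-variable rule is the only normality rule defined, no difference variable exists, and nothing requires the same summary at each visit. The absence of a change estimate and interval does not depend on how the rule is read.

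Three stronger readings are tempting and are not supported:
- That chi-square is prescribed for continuous characteristics, or that cut-points are forced. The text names no continuous characteristic and no split. It gives one test for characteristics of unrestricted type and omits any method for continuous ones.
- That visit summaries use everyone with a value while the test uses only pairs. The plan does not say who enters the summaries.
- That the p-values would be seriously wrong. The low disagreement between the two tests argues against this.

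**Conclusion.** The point holds as a fault of specification. Read naturally, the plan selects the paired test from visit values and can set a mean beside a median. On any reading it plans no within-patient change or confidence interval for an objective that is about change.

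The 9.5% and 14.25% figures need only normality and independent tests. The larger percentages, and the size of the display error, rest on assumed shapes and correlation. The distortion runs from about 1 unit (HDL-like) to about 36 cells (CD4-like), and in the CD4-like case mixing of summaries falls to 9% at n = 169. The consequence for significance testing is small. The rapid-onset comparison has a related gap: no test is named for continuous characteristics. This is a secondary point, but worth correcting before the analysis because correction is nearly free.

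**What to change.** In Paraclinical Results:
- For each biomarker, report the within-patient change (week 24 minus baseline, and week 48 minus baseline) with a 95% CI in patients with both values, and show the visit summaries for those same pairs.
- Prespecify one summary per biomarker and use it at all visits.
- Do not let a per-visit Shapiro-Wilk test choose the summary or the paired test. If a distribution check is kept, apply it to the differences. Name the Wilcoxon signed-rank test explicitly.

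In Rapid Onset of Therapy, limit chi-square to categorical characteristics, with Fisher's exact test when expected counts are below 5, and use a two-sample t-test or rank-sum test for continuous ones.

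With one fixed summary per marker, the chance of a mean at one visit beside a median at another falls to zero. The cost is a few sentences of analysis-plan text. No new data are needed, and the methods are available in the software already named.

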- 4. Non-Infectious Manifestations: HIV is also linked to a range of non-infectious complications due to chronic immune activation and systemic inflammation. These include cardiovascular, hepatic, renal, bone, and neurological diseases. Cardiovascular disease in HIV patients may manifest as coronary artery disease, dilated cardiomyopathy, pulmonary hypertension, and endothelial dysfunction. Liver complications may involve virus-associated viral hepatitis and drug-induced hepatotoxicity, while renal dysfunction can present as HIV-associated nephropathy (37-39).
- 5. Hematological Manifestations: These are common and may include anemia, leukopenia, and thrombocytopenia. These conditions may result from the direct infection of hematopoietic progenitor cells, bone marrow dysfunction, and activation of the reticuloendothelial system (40).
- 6. Immune Reconstitution Inflammatory Syndrome (IRIS): In patients initiating ART, a paradoxical exacerbation of underlying infections may occur due to partial recovery of the immune system. IRIS can complicate clinical management and requires careful monitoring (24,41). In some cases, ART initiation should be postponed for a few weeks, especially when diagnosing opportunistic infections such as cytomegalovirus disease or meningeal cryptococcosis, to avoid exacerbation or worsening of symptoms, which can lead to considerable morbidity

and mortality.

Diagnosis of HIV

HIV diagnosis is performed using a combination of tests that detect viral RNA, p24 antigen, and HIV-specific antibodies. This approach allows for the identification of both acute and chronic infections:

- 1. HIV RNA: Detection of viral RNA is possible approximately 10-12 days after exposure to the virus, making this test particularly useful in the acute phase of infection, when antibodies are not yet detectable (23).
- 2. p24 Antigen: The p24 antigen appears in serum or plasma about 15-17 days after exposure. Detection of p24 antigen is a key feature of fourth- and fifth-generation tests, which allow for the identification of infection before antibodies develop (5,23).
- 3. Specific Antibodies: HIV antibodies (IgM and IgG) are detectable in serum or plasma approximately 21 days after exposure. Today, fourth-generation tests combine antibody detection with p24 antigen detection, improving sensitivity and enabling earlier detection of infection (5,42,43).

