Bictegravir is a second-generation integrase strand transfer inhibitor (INSTI) used in HIV treatment. It is a key component of BikARVTy®, a fixed-dose regimen combining bictegravir, emtricitabine, and tenofovir alafenamide in a single daily tablet (52,53). This drug is notable for its high genetic barrier to resistance, meaning the virus is less likely to develop resistance to it compared to other INSTIs such as raltegravir and elvitegravir (54,55). It also has a limited drug-drug interaction profile, making it suitable for use in

combination with other antiretrovirals (52,56).

In phase 3 clinical trials, the bictegravir/emtricitabine/tenofovir alafenamide regimen has been shown to be non-inferior to dolutegravir-based regimens in both treatment-naïve and treatment-experienced patients, achieving effective virologic suppression without the emergence of resistance (53,57,58). Additionally, it is well tolerated and does not require prior HLA-B*5701 testing, which facilitates its rapid initiation in HIV treatment (53,57).

The most common adverse effects reported in clinical trials include diarrhea, nausea, and headache, with an incidence of at least 5% in treated subjects (59). Other less frequent adverse effects (\geq 2%) include fatigue, abnormal dreams, dizziness, insomnia, and abdominal distension (59). Regarding laboratory abnormalities, increases in serum creatinine, which stabilized throughout treatment, and increases in total bilirubin, mainly grade 1 and 2, were observed. Most adverse events were grade 1, and discontinuations due to adverse events were uncommon (59). Psychiatric events, such as suicidal ideation and depression, have also been reported, particularly in subjects with a history of psychiatric conditions. In subjects with end-stage renal disease, serious adverse events such as pneumonia and fluid overload were observed (59).

Objectives

General Objective: To estimate the clinical effectiveness and safety of HIV-positive patients on TAF/FTC/BIC treatment within an EPS in Colombia.

Specific Objectives:

- To characterize the sociodemographic and clinical profile of patients with HIV who initiate antiretroviral therapy with TAF/FTC/BIC.
- To identify the proportion of patients who have been on different pretreatment regimens before initiating TAF/FTC/BIC therapy.
- To assess the proportion of patients achieving virologic suppression at weeks 24

and 48 following the initiation of TAF/FTC/BIC therapy.

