LDL value at week 48	Low-density lipoprotein value at week 48 (+ or - 2 weeks) of TAF/FTC/BIC therapy	Quantitative, continuous	1, 1.5, 1.8, 2, n	
AST at baseline	The patient has aspartate aminotransferase results at baseline (+ or - 4 weeks) of TAF/FTC/BIC therapy.	Qualitative	0: No 1: Yes	
AST at baseline value	Aspartate aminotransferase value at baseline (+ or - 4 weeks) of TAF/FTC/BIC therapy	Quantitative, continuous	1, 1.5, 1.8, 2, n	
AST at week 24	The patient has aspartate aminotransferase results at week 24 (+ or - 2 weeks) of TAF/FTC/BIC therapy.		0: No 1: Yes	
AST value at week 24	Aspartate aminotransferase value at week 24 (+ or - 2 weeks) of TAF/FTC/BIC therapy	Quantitative, continuous	1, 1.5, 1.8, 2, n	

AST at week 48	The patient has aspartate aminotransferase results at week 48 (+ or - 2 weeks) of TAF/FTC/BIC therapy.	Qualitative	0: No 1: Yes	
AST value at week 48	Aspartate aminotransferase value at week 48 (+ or - 2 weeks) of TAF/FTC/BIC therapy	1, 1.5, 1.8, 2, n		
ALT at baseline	The patient has alanine aminotransferase results at baseline (+ or - 4 weeks) of TAF/FTC/BIC therapy.	Qualitative	0: No 1: Yes	
ALT value at baseline	Alanine aminotransferase value at baseline (+ or - 4 weeks) of TAF/FTC/BIC therapy	Quantitative, continuous	1, 1.5, 1.8, 2, n	
ALT week at 24	The patient has alanine aminotransferase results at week 24 (+ or - 2 weeks) of TAF/FTC/BIC therapy.	Qualitative	0: No 1: Yes	
ALT value week at 24	Alanine aminotransferase level at week 24 (+ or – 2 weeks) of TAF/FTC/BIC therapy	Quantitative, continuous	1, 1.5, 1.8, 2, n	
ALT week at 48	The patient has alanine aminotransferase		0: No 1: Yes	
ALT value at week 48	Alanine aminotransferase value at week 48 (+ or - 2 weeks) of therapy with TAF/FTC/BIC.	1, 1.5, 1.8, 2, n		
Total bilirubin at baseline	aseline The patient has total bilirubin results at baseline (+ or - 4 weeks) of therapy with Qualitative TAF/FTC/BIC.			
Total bilirubin value at	ubin value at Total bilirubin value at baseline (+ or - 4		1, 1.5, 1.8, 2, n	
baseline	weeks) of therapy with TAF/FTC/BIC.	continuous	, -, -, ,	
Total bilirubin at week 24	The patient has total bilirubin results at week 24 (+ or - 2 weeks) of therapy with TAF/FTC/BIC.	Qualitative	0: No 1: Yes	
Total bilirubin value at at week 24	Total bilirubin value at week 24 (+ or - 2 weeks) of therapy with TAF/FTC/BIC.	Quantitative, continuous	1, 1.5, 1.8, 2, n	

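### Safety is a stated aim, but no analysis commits to reporting on-treatment liver tests or deaths, and renal markers are analysed only as average change from baseline

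*Combined protocol and SAP*

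**What the plan says.** The general objective is "To estimate the clinical effectiveness and safety of HIV-positive patients on TAF/FTC/BIC treatment within an EPS in Colombia". The background on the regimen, under HIV Treatment, describes two laboratory findings: "increases in serum creatinine, which stabilized throughout treatment" and "increases in total bilirubin, mainly grade 1 and 2, were observed".

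The Variables table has a presence flag and a value for AST, ALT and total bilirubin at each of three times; the last ALT row, for example, is defined as "Alanine aminotransferase value at week 48 (+ or - 2 weeks) of therapy with TAF/FTC/BIC". The table also has a death indicator, "The patient passed away after the index date", and a date of death.

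Under Specific Objectives, the one laboratory objective other than viral suppression is limited to CD4 count, renal function and lipids. The matching Statistical Analysis subsection, "Paraclinical Results: CD4 T-Lymphocytes, Renal Function, and Lipid Profile", has the same three topics. It compares the baseline mean or median with the values at weeks 24 and 48, by paired t-test or Wilcoxon test. It defines no threshold, grade or proportion. The adverse-event subsection promises a classification by type and severity, but names no laboratory abnormality, no grading scale and no death.

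**The concern.** A reader of the results will expect a study with safety in its general objective to say what happened to liver tests and how many patients died. The data will be in the database, but nothing in the plan obliges anyone to tabulate them. If they are tabulated later, the cut-offs could be chosen after the data have been seen.

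For the kidney the gap is narrower. Creatinine and eGFR will be reported, but a laboratory safety signal usually lies in a few patients who change a lot, and a shift in the average is a poor detector of that. The cohort is small, and patients who stopped treatment before six months are excluded, so those who stopped early because of toxicity may already be missing. Laboratory values and deaths among those retained are then much of the remaining safety evidence.

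**Working it through.** The study is a census with no sample-size or power calculation, so there is no figure in the plan to reproduce. The check sets the variables against the objectives and analyses; the arithmetic after it is illustrative.

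**Variables against analyses**

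| Collected | Named for this regimen in the background? | Specific objective | Analysis subsection |
|---|---|---|---|
| Total bilirubin, 3 times | Yes | None | None |
| AST and ALT, 3 times | No; "drug-induced hepatotoxicity" appears only among HIV-related liver complications in general | None | None |
| Creatinine and eGFR, 3 times | Creatinine yes | Yes (renal function) | Mean or median against baseline only |
| Death and date | No | None | None |

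**Volume.** 3 liver tests × 3 times = 9 values per patient, and 9 × 169 = 1,521. The 169 is the number prescribed the regimen in 2020 to 2023, so both figures are maxima before exclusions and missing results.

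**What a median shows.** With n = 169 the median is the value of rank (169 + 1)/2 = 85. If 5 patients move to one extreme and the rest do not change, the new median lies at most 5 ranks from the old one, however large those 5 changes are.

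**What a mean shows.** These inputs are assumptions, not from the documents: baseline eGFR 90; affected patients lose 30%, that is 27 units; the others do not change on average; SD of their change, sd, is 8 to 15; n = 169. With affected fraction f:
- mean shift = 27f
- SD of all changes = √(sd² + f(1 − f) × 27²)
- power ≈ Φ(shift × √169 / SD − 1.96), two-sided 5%

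| f | Patients | Mean shift | Power, sd 8 | Power, sd 15 |
|---|---|---|---|---|
| 5% | about 8 | 1.35 | 42% | 19% |
| 2% | about 3 | 0.54 | 12% | 7% |

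For f = 5% and sd = 8: SD = √(64 + 0.0475 × 729) = 9.93, then 1.35 × 13/9.93 − 1.96 = −0.19, and Φ(−0.19) = 42%.

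**What a proportion shows (exact 95% limits, n = 169)**
- 0 patients: upper limit 2.16%
- 3 patients: 1.8% (0.37% to 5.10%)
- 5 patients: 3.0% (0.97% to 6.77%)
- 8 patients: 4.7% (2.07% to 9.11%)

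The same 8 patients who move the mean by 1.35 units are thus reported directly as a rate with an interval. As a hypothetical liver case, if 5 of 169 had a fivefold ALT rise from equal baselines and the rest did not change, the mean would rise by (164 + 25)/169 − 1 = 12%, the median would hardly move, and the count would give 3.0%. Extending the averages to liver tests is therefore not enough without the counts.

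**The case against.** Several points on the other side are fair.

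- **General text could cover part of the gap.** The descriptive rule for the sociodemographic and clinical profile lists no variables and plausibly reaches baseline liver values. The adverse-event subsection could be stretched to laboratory events or deaths. This stands as far as it goes, but neither text commits to on-treatment liver values or to deaths. Apart from death, the only dedicated event variables are three ungraded emergency-visit flags.
- **Creatinine is analysed.** A reader might infer that the laboratory risks named for the regimen would all go unreported. The documents do not support that: creatinine falls under renal function. Only bilirubin is both named and without an analysis, and AST and ALT rises are not named as risks of this regimen.
- **Stabilisation can be partly read from the plan.** A reader might also infer that the plan cannot tell an early stable creatinine rise from a progressive one. That is too strong. Baseline is compared with both week 24 and week 48, and similar shifts at both suggest stability. Only a direct paired comparison of the two weeks is missing.
- **The death fields may serve another purpose.** They follow the insurance-termination fields and may be meant as follow-up status. The documents do not say, so it cannot be claimed that they have no use, only that no mortality result is planned.
- **Threshold counts go beyond a descriptive objective.** This has some force for the renal part. It does not answer the safety aim, for which an average alone is weak.

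**Conclusion.** The gap is real and should be closed, but it is one of commitment in the specific objectives and the analysis; the plan does not rule these results out. On-treatment AST, ALT and bilirubin and all deaths lack a named analysis, and bilirubin is the clearest case. Creatinine and eGFR will be reported, but in a form that would miss a few patients with marked deterioration.

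The size is illustrative. The power figures rest on the assumed eGFR values, the ALT case is hypothetical, and 169 patients and 1,521 values are ceilings. The conclusion about committed reporting needs none of these numbers; it follows from comparing the Variables table with the objectives and analyses.

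One related point is open: the documents do not say whether a death before six months counts as discontinuation under the exclusion criteria. If it does, early deaths drop out and any mortality count to week 48 is too low.

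**What to change.** In Specific Objectives and Statistical Analysis:

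1. Add AST, ALT and total bilirubin to the laboratory objective, and extend the paired baseline-to-week-24 and baseline-to-week-48 analysis to them.
2. For liver tests, creatinine and eGFR, report the number and proportion of patients whose grade worsens from their own baseline, on a named laboratory grading scale fixed before extraction. Include patients already abnormal at baseline; counting only moves from normal to abnormal would miss worsening in patients with the chronic kidney disease or hepatitis B or C that the study records. Give exact 95% intervals, denominators and missing counts at each time.
3. Report the number of deaths from the index date to week 48, and later deaths separately. State whether patients who died before six months are kept despite the exclusion for stopping before six months.
4. Optionally, add the paired week-24-to-48 change in creatinine and eGFR as a direct check of stabilisation. This is a refinement and does not correct an error.

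The cost is a few more tables from variables already being extracted, plus recording laboratory reference limits, which the Variables table does not now include. No new patients or procedures are needed.
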